6. STUDY POPULATION

6.1 INCLUSION CRITERIA

In order to be eligible to participate in this study, an individual (or their legal guardians as applicable) must meet all of the following criteria:

1. Parent(s) or guardian(s) willing and able to provide consent prior to initiation of any study procedures
2. Stated willingness of parent(s) or guardian(s) to comply with all study procedures and availability for the duration of the study
3. Malaria comprehension exam completed by parent(s) or guardian(s) and passed with a score of $\geq 80\%$ or per investigator’s discretion
4. Healthy children 6-10 years of age at enrollment (inclusive)
5. Parent(s) or guardian(s) are able to provide proof of identity to the satisfaction of the study clinician completing the enrollment process
6. Willing to have blood samples stored for future research

6.2 EXCLUSION CRITERIA

An individual who meets any of the following criteria will be excluded from participation in this study:

1. Medical, behavioral, cognitive, or psychiatric disease that in the opinion of the investigator affects the ability of the participant's parent and/or legal guardian to understand and comply with the study protocol
2. Menstruating females (in order to avoid cultural implications of further assessing pregnancy potential i.e. sexual activity in this age group)
3. Hemoglobin (Hgb), WBC, absolute neutrophils, and platelets outside the local laboratory-defined limits of normal and \geq Grade 2 (subjects may be included at the investigator's discretion for 'not clinically significant' abnormal values)
4. Alanine transaminase (ALT) or creatinine (Cr) level above the local laboratory-defined upper limit of normal and \geq Grade 2 (subjects may be included at the investigator's discretion for 'not clinically significant' abnormal values)
5. Infected with human immunodeficiency virus (HIV), hepatitis B, or hepatitis C
6. Sickle cell disease by history
7. Taking or planning to take seasonal malaria chemoprophylaxis
8. Clinically significant abnormal electrocardiogram (ECG) such as abnormal QTc
9. History of receipt of the following:
 - Investigational malaria vaccine in the last 2 years
 - Immunoglobulins and/or blood products within 6 months of enrollment
 - Investigational product within 3 months of enrollment
 - Chronic (\geq 14 days) oral or IV corticosteroids (excluding topical or nasal) at immunosuppressive doses (i.e., prednisone \geq 20 mg/day or equivalent) or immunosuppressive drugs within 30 days of enrollment
 - Live vaccine within 30 days of enrollment
 - Killed vaccine within 14 days of enrollment or planned receipt of a killed vaccine within 14 days of scheduled vaccination
10. Known medical problems:
 - Pre-existing autoimmune or antibody-mediated diseases (e.g. systemic lupus erythematosus, rheumatoid arthritis, multiple sclerosis, Sjögren's syndrome, or autoimmune thrombocytopenia)
 - Severe asthma (defined as asthma that is unstable or required emergent care, urgent care, hospitalization, or intubation during the past two years, or that has required the use of oral or parenteral corticosteroids at any time during the past two years)
 - Immunodeficiency disorder
 - Asplenia or functional asplenia
 - Diabetes
 - Deep venous thrombosis or thromboembolic event
 - Seizures (exception is simple febrile seizures during childhood)
11. Evidence of clinically significant neurologic, cardiac, pulmonary, hepatic, endocrine, rheumatologic, autoimmune, hematological, oncologic, or renal disease by history, physical examination, and/or laboratory studies
12. History of a severe allergic reaction or anaphylaxis following previous vaccinations or medications
13. Known allergies or other contraindications against: artemether-lumefantrine, PfSPZ Vaccine, or human serum albumin

14. Current or planned participation in an investigational vaccine study through the last required protocol visit.
15. Other condition(s) that, in the opinion of the investigator, would jeopardize the safety or rights of a participant participating in the trial, interfere with the evaluation of the study objectives, or would render the subject unable to comply with the protocol

6.3 INCLUSION OF VULNERABLE PARTICIPANTS

6.3.1 Participation of family members of study team members

Family members of study team members may be enrolled in this study as this population meets the study entry criteria. Neither participation nor refusal to participate as a subject in the research will have an effect, either beneficial or adverse, on the participant's family members employment.

Every effort will be made to protect participant information, but such information may be available in medical records and may be available to authorized users outside of the study team in both an identifiable and unidentifiable manner.

6.4 INCLUSION OF PREGNANT WOMEN, FETUSES OR NEONATES

This trial will not include pregnant women, fetuses, or neonates as they are outside the targeted population age range.

6.5 LIFESTYLE CONSIDERATIONS

Not applicable.

6.6 SCREEN FAILURES

Screen failures are defined as participants who consent to participate in the clinical trial but are not subsequently enrolled in the study due to failure to satisfy eligibility criteria. A minimal set of screen failure information is required to ensure transparent reporting of screen failure participants, to meet the Consolidated Standards of Reporting Trials (CONSORT) publishing requirements and to respond to queries from regulatory authorities. Minimal information includes demography, screen failure details, eligibility criteria, and any serious adverse event (SAE).

Individuals who do not initially meet the criteria for participation in this trial (screen failure) because of an abnormal vital sign, laboratory, or ECG finding that may be transient (e.g., secondary to acute illness) may be rescreened at the principal investigator's (PI's) discretion. Rescreened participants will maintain the same participant number as for the initial screening.

6.7 STRATEGIES FOR RECRUITMENT AND RETENTION

6.7.1 Costs

There is no cost to subjects for taking part in this trial.

6.7.2 Compensation

Subjects will be given in kind (such as rice and/or millet) or cash equivalent, that can be given in multiple installments if preferred (e.g. for screening, at each vaccination visit, and periodically through the natural human malaria infection [NHMI] period), to compensate for the time taken to come to the study clinic for study-related visits. Preferred compensation will be decided in

consultation with village elders, but based on past studies in the community rice, millet, or cash have been acceptable.

The amount equals US \$6 or US \$3 for each visit depending on the time spent by the volunteer. Families will receive US \$6 for visits with multiple procedures, venous blood draws, and longer study visits while US \$3 for brief visits and limited blood draws and/or procedures. Unscheduled visits for clinical care only (no research sample collection or procedures) will not be compensated. Volunteer compensation payments will be made periodically throughout the study.

Table 11. Estimated compensation for the study.

Study Group	US Dollar Equivalent	Rice or Millet Dispensed or Cash equivalent (Local Currency [CFA]) ^A
All arms	\$123	61,000 CFA

^A Assuming currency exchange rate of US \$1= 500 CFA; current (April 2021) conversion US \$1 = 500 CFA.

7. STUDY INTERVENTION

7.1 STUDY INTERVENTION(S) ADMINISTRATION

7.1.1 Study Intervention Description

PfSPZ Vaccine

The vaccine referred to as PfSPZ Vaccine contains aseptic, purified, vialized, cryopreserved, radiation attenuated NF54 *Pf* sporozoites (PfSPZ) produced by Sanaria Inc. PfSPZ Vaccine is manufactured in compliance with Good Manufacturing Practice (GMP) regulations (21 Code of Federal Regulations [CFR] 21), that is described in detail in Investigational New Drug

. Manufacture of PfSPZ Vaccine is performed in Sanaria's Clinical Manufacturing Facility (CMF) in Rockville, Maryland, USA. The PfSPZ Vaccine manufacture is an aseptic process. In

process testing includes sterility testing according to USP<71>. In brief, manufacture includes disinfection of mosquito eggs, which are inoculated into vented flasks containing growth medium. The eggs hatch and develop into pupae, which are transferred to an adult mosquito container where the adult mosquitoes emerge. In vitro culture of Pf parasites is initiated from a working cell bank (WCB) vial of Pf isolate NF54, which is described in detail in Biologics

Master File . The asexual parasite stages are induced to produce gametocytes. The

aseptic adult mosquitoes are fed a *P. falciparum* gametocyte-infected blood meal through an artificial membrane. Infected adult mosquitoes are maintained and sporozoites migrate to the salivary glands in two weeks from the time of infectious feed. The PfSPZ in the mosquito salivary glands are attenuated by irradiation at 150 Gy. The salivary glands of infected mosquitoes are harvested by manual dissection. Salivary glands are then dissociated to release the PfSPZ that are then purified and formulated to form PfSPZ Vaccine bulk product prior to cryopreservation. Cryopreservation commences with the addition of cryoprotective additives to the PfSPZ Vaccine bulk product to produce the PfSPZ Vaccine final product. The final product

is dispensed into vials that are stored in liquid nitrogen vapor phase (LNVP) at -150°C to -196°C. All the procedures are described in detail in the cross-referenced IND .

Diluent

The diluent for PfSPZ Vaccine is composed of phosphate-buffered saline (PBS) and about 1% human serum albumin (HSA). HSA is a licensed product which is approved for parenteral, IV administration to humans and is purchased by Sanaria Inc. Diluent is released with a Certificate of Analysis (CoA), and is placed on a stability program. Vials of diluent will be shipped to the clinical site.

PBS that will be used was manufactured in compliance with GMP by Sanaria Inc. ([name], Rockville, MD, USA). A Certificate of Analysis (CoA) is generated for each lot of PBS that is released for use in clinical studies. In addition, the PBS lots are placed on stability.

HSA is a licensed product which is approved for parenteral, IV administration to humans and is purchased by Sanaria Inc. The HSA is repackaged at Sanaria. Repackaged HSA is released with a CoA.

0.9% Sodium Chloride Normal Saline (NS) (Placebo)

Sterile isotonic 0.9% sodium chloride (normal saline (NS)) will be procured in the US and shipped to Mali at ambient temperature. Like the vaccine product, NS is a clear liquid, making it indistinguishable when drawn up into a syringe. NS will be used as a placebo, rather than a comparator vaccine, as currently there are no licensed vaccines available as IV formulations.

Artemether Lumefantrine (AL)

Artemether-lumefantrine (AL) will be administered approximately 1-2 weeks prior to the first and perhaps third dose of PfSPZ Vaccine or normal saline. AL will be purchased from a licensed pharmacy in Mali from a single manufacturer and lot number.

7.1.2 Dosing and Administration

PfSPZ Vaccine + Diluent

The dose of PfSPZ Vaccine administered to vaccinees is 9×10^5 PfSPZ in a range 0.25 to 0.5 mL of diluent. The dose of NS is likewise 0.5 mL. Each product is a clear, non-viscous liquid that has no perceptible color or odor. Each product is received by the blinded clinical vaccine administration team in syringes that appear identical in every way with labels and documents that ensure blinding of the clinical vaccine administration team but clear tracking of volunteers and syringes. Each is administered by DVI. PfSPZ Vaccine, diluent and NS will be shipped by Sanaria to the study site in Mali, where it will be received by Pharmaceutical Operations staff.

The syringes are prepared by the unblinded Pharmaceutical Operations team following SOPs. The preparation area is not accessible by clinical staff during syringe preparation or at any time when the unblinded randomization list is being reviewed. After preparation, the filled syringes are provided to the clinical team for DVI. The Pharmaceutical Operations team does not interact with study participants. The maximum allowable time between thawing of a PfSPZ Vaccine vial and injection is 30 minutes.

To perform DVI, a superficial vein in the arm or hand is located, prepped for venipuncture, a restricting band is placed on the arm, the needle is inserted into the vein, the plunger is

withdrawn slightly to cause blood flashback thereby confirming successful venous entry, the restricting band is removed, and the contents of the syringe are injected over a few seconds. Hemostasis is achieved by immediate direct pressure after withdrawing the needle. The syringe and needle are discarded into a sharps/biohazard container. The subject is then transferred to the observation area.

During administration of PfSPZ Vaccine, advanced-life-support drugs and resuscitation equipment will be immediately available for the management of anaphylaxis. The study staff administering PfSPZ Vaccine will wear gloves. The subject will stay in the clinical area for at least 30 minutes after vaccine administration.

0.9% sodium chloride Normal Saline (NS) (Placebo)

NS will be injected by needle and syringe into a peripheral vein by a qualified member of the clinical team. NS will be prepared such that a defined volume will appear indistinguishable from PfSPZ Vaccine.

During administration of NS, advanced-life-support drugs, trained personnel, and resuscitation equipment will be immediately available for the management of anaphylaxis. The study staff administering NS will wear gloves. The subject will stay in the clinical area for at least 30 minutes after vaccine administration.

Artemether Lumefantrine

All antimalarial medications used for the study will be maintained at the study site and administered by direct observational therapy (first dose) by a study team member. AL (and other antimalarials) will be purchased from commercial sources as detailed above and provided by the MRTC study team to subjects for dosing around vaccination only.

7.2 PREPARATION/HANDLING/STORAGE/ACCOUNTABILITY

7.2.1 Acquisition and Accountability.

PfSPZ Vaccine

PfSPZ Vaccine is manufactured and released for use by Sanaria Inc. Sanaria will supply the investigational product, diluent and NS placebo to the clinical site. Syringes will also be supplied by Sanaria Inc. The pharmacist at the study site will ensure that all investigational products are inventoried and stored as indicated in the relevant SOP. Accurate records will be maintained regarding receipt of PfSPZ Vaccine, diluent and NS, as well as syringes which include: date received, lot number, amount received and disposition.

Sanaria will receive copies of document records in parallel regarding disposition of product, which include:

- Participant identification number
- Date and time PfSPZ Vaccine vial is thawed and time PfSPZ Vaccine is inoculated.
- Volume injected
- Lot number
- Signature of the person preparing the syringe
- Signature of the verifier
- Signature of the person administering the injection

- Signature of the verifier

Any partly used vials of PfSPZ Vaccine, NS, as well as empty vials, will be destroyed according to the applicable SOP and as determined by Sanaria. An inventory of the number of vials shipped versus used will be recorded. Unthawed and unopened vials of PfSPZ Vaccine and unused and unopened diluent vials and NS vials will be inventoried and returned to Sanaria.

PfSPZ Vaccine is not a licensed product and must be distributed under an Investigational New Drug Application (IND) in accordance with FDA regulations. The product must be administered by or under the supervision of the principal investigator or a subinvestigator of the clinical study, with the exception of syringe preparation which is delegated to the Pharmaceutical Operations team. Sanaria personnel will provide oversight of the syringe preparation work performed by the Pharmaceutical Operations team.

The clinical site must confirm that the vials of PfSPZ Vaccine have been transported and stored below -150°C according to SOP. Immediately prior to use, the cryovials will be thawed by trained Pharmaceutical Operations staff.

All PfSPZ Vaccine vials that are used will be documented on inventory forms as well as documented disposition forms according to SOP. All unused PfSPZ Vaccine vials will be returned to Sanaria Inc.

Diluent

The Diluent is phosphate buffered saline (PBS) containing human serum albumin (HSA). Diluent will be provided to the clinical sites by Sanaria Inc. The clinical site must confirm and document that the vials of diluent have been transported and stored within specified ranges. All diluent vials that are used will be documented on inventory forms as well as documented disposition forms according to SOP.

Diluent vial accountability will be maintained to document chain of custody from Sanaria Inc., to study site. An inventory to account for number of vials used will be recorded and kept in the study file. All unused diluent vials will be returned to Sanaria Inc.

0.9% Sodium Chloride Normal Saline (NS) (Placebo)

The clinical site will confirm and document that the vials of NS have been transported and stored within specified ranges.

NS accountability will be maintained to document chain of custody from Sanaria Inc., to study site. An inventory to account for number of vials dispensed for each subject injection will be recorded and kept in the study file. All unused NS vials will be returned to Sanaria Inc.

Artemether Lumefantrine

Dosing of artemether lumefantrine will be used according to the package label.

7.2.2 Formulation, Appearance, Packaging, and Labeling

PfSPZ Vaccine

PfSPZ Vaccine is a suspension of aseptic, purified, metabolically active, non-replicating (live, radiation attenuated) cryopreserved Pf sporozoites (PfSPZ) formulated in cryoprotectant and

dispensed in vials. PfSPZ Vaccine is stored in liquid nitrogen vapor phase (LNVP) at -150°C to -196°C, thawed, diluted in diluent and administered by DVI.

Each cryovial is labeled indicating that it contains PfSPZ Vaccine, together with the lot number and date of manufacture.

The label for PfSPZ Vaccine reads as follows:

Label Name	Actual Size	Enlarged Size
Lot#XXXXXX	
PfSPZ (NF54) VACCINE SANARIA® Lot#XXXXXX Manufactured: MMM YYYY
 
SINGLE DOSE VIAL 900,000 SPZ in 0.02 mL Store in liquid nitrogen vapor phase Caution: New Vaccine Ltd by Federal Law to Investigational Use Only
	
PfSPZ (NF54) VACCINE SANARIA® Lot#XXXXXX Manufactured: MMM YYYY
 
SINGLE DOSE VIAL 900,000 SPZ in 0.02 mL Store in liquid nitrogen vapor phase Caution: New Vaccine Ltd by Federal Law to Investigational Use Only

0.9% Sodium Chloride Normal Saline (NS) (Placebo)

The NS to be used in this trial will be an FDA licensed product which is commercially available (0.9% sodium chloride for injection 10 mL by Pfizer⁴). NS will be purchased by Sanaria and supplied to the clinical site.

Artemether Lumefantrine

The artemether lumefantrine used in this trial will be an FDA licensed product which is commercially available, purchased from a licensed pharmacy in Mali, and used according to the package label.

7.2.3 Product Storage and Stability

PfSPZ Vaccine

PfSPZ Vaccine is cryopreserved in aliquots of 20 µL in 0.5 mL cryovials and stored in LNVP at below -150°C. The cryovials are packaged in a latched box and transported from Sanaria Inc. to the clinical study site in a LNVP dry shipper. The LNVP dry shipper has a holding time of at least 10 days. The PfSPZ Vaccine remains in the dry shipper at the clinical study site and individual cryovials are removed from the dry shipper and thawed as needed for PfSPZ Vaccine dilution, syringe preparations and immunizations. Each cryovial is labeled indicating that it contains PfSPZ Vaccine, together with the lot number and date of manufacture. The LNVP dry shipper is labeled to indicate it is approved by International Air Transport Association (IATA) for shipment by air, conforms to UN3373 for Biological Substance, Category B, and packing instructions 650 (US 49 CFR, Part 173.199).

Transfer, receipt and maintenance of PfSPZ Vaccine from its storage site to the clinical trial site will follow SOP331 (Cryopreserved Material Transportation), provided by Sanaria Inc. At the study site, the LNVP shipper will be continuously monitored by a data logger as well as a

⁴ <https://www.medline.com/product/Sodium-Chloride-For-Injection-10ml-by-Pfizer/Z05-PF30165>

temperature probe according to Sanaria standard operating procedure (SOP). Receipt of the products will be documented on a tracking log by trained study staff according to Sanaria SOP.

Diluent

The Diluent is stored at ambient temperature within specifications (between 15°C to 30°C) that is monitored by a continuous data logger in a controlled access room. Receipt of the products will be documented on a tracking log by trained study staff according to Sanaria SOP.

0.9% Sodium Chloride Normal Saline (NS) (Placebo)

The NS is stored at room temperature in a controlled room per product standards. Each NS vial can either be single use or multi-use if used in a biological safety cabinet to maintain asepticity over a period of a few hours (i.e. the duration of vaccine preparation on a given day).

Artemether Lumefantrine

AL tablets will be maintained in the manufacturer's original packaging and stored at the clinic under recommended storage conditions until prepared for dispensing.

7.3 MEASURES TO MINIMIZE BIAS: RANDOMIZATION AND BLINDING

7.3.1 Randomization

Randomization will occur in blocks at 1:1 into vaccine or placebo arms. Randomization will be assigned at the time of first artemether/lumefantrine dose with the next available subject. Once a subject has received their first vaccination, they cannot be replaced.

During the study, the list linking randomization numbers to study product (PfSPZ Vaccine or control) will be made available only to the study statistician and associated team members, pharmaceutical operations team/syringe preparers (at the start of the study), independent safety monitor (if needed to review), and DSMB chair (if needed for closed session unblinded review). On vaccination days, the vaccines associated with each randomization number will be obtained from the head of pharmaceutical operations.

If a subject is given the wrong treatment at V1 due to an allocation error, the same vaccine will be administered at V2 and V3 so long as the error is identified before the timing of the next injection. In the situation where an eligible participant already assigned a randomization number becomes ineligible during the window between randomization number assignment and administration of V1 (e.g., as a result of new information about the participant, withdrawal from participation, or other factors), a replacement will not be assigned, and the randomization number will not be assigned to another participant. This occurrence is anticipated to be a rare event.

7.3.2 Blinding

The study is double-blind (clinical staff and participants). Blinding extends to the parents and/or guardians of pediatric participants, to laboratory staff conducting clinical chemistry, hematology, and parasitology tests, and to laboratory staff conducting research assays such as antibody and cellular immunity assays. Blinding will continue until completion of the last study visit and the cleaning and locking of the data set. The principal investigator will be responsible for strict maintenance of the blinding on site.

7.3.3 Unblinding

Details of unblinding procedures are provided in the unblinding SOP. An overview is provided here.

Unblinding of individual participants: If knowledge of the treatment assignment is needed to provide appropriate medical care, and unblinding is recommended by the principal investigator, the local safety monitor (LSM), or the DSMB, the treatment assignment of that research subject may be unblinded and provided to the treating clinician and other clinical staff on a need-to-know basis by the head of Pharmaceutical Operations at the study site or other designated unblinded staff who have access to the unblinded randomization list and pharmaceutical team records. The principal investigator must contact the Sponsor and provide documentation of the event and the reasons for unblinding.

If pausing criteria are met based on blinded data, the following procedure will be followed, as described in **Section 7.1.1**. The principal investigator (who remains blinded) will provide the list of research subjects contributing to pausing criteria to the head of Pharmaceutical Operations or their designee, and will also inform the head of Pharmaceutical Operations how many of these research subjects have to be vaccine recipients (as opposed to NS recipients) in order to know if pausing criteria have truly been met. The head of Pharmaceutical Operations will then privately identify the treatment assignment of each participant on the list, and then inform the principal investigator if the pausing criteria have been met, but will not unblind the principal investigator with respect to individual participants.

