- Five percent or more of the vaccinees enrolled at any time point in one arm (calculated as 5% of the vaccinees in the full study roster enrolled to date, as long as there are at least three subjects with the AE) experience the same severe (grade 3) AE during the periods of AE collection deemed possibly, probably or definitely related to study product administration (PfSPZ Vaccine or NS), or experience the same grade 3 laboratory abnormality on day V2 + 14 or day V3+14. Grade 3 AEs deemed possibly, probably or definitely related to malaria (as opposed to PfSPZ Vaccine or to NS) will not count toward meeting this criterion. The site, where clinical staff are blinded, can only monitor total populations (vaccine plus placebo recipients) and if a 5% threshold is reached, unblinded study staff (e.g., the head of Pharmaceutical Operations) will need to confirm that the total indeed constitutes 5% of vaccinees. Note that we have considered using Grade 2 rather than Grade 3 laboratory abnormalities, but drops in hemoglobin, neutrophils, platelets and sometimes other blood count indices meeting Grade 2 criteria for severity are common in African pediatric populations.
- One participant experiences an SAE deemed possibly, probably or definitely related to study product. This criterion will not be met if it turns out that the participant received NS. SAEs related to malaria or to antimalarial treatment which are expected, will be reported expeditiously but will not fulfill this criterion. If the SAE is unexpected with respect to malaria or antimalarial treatment, it will fulfill the criterion.

If either of these criteria appear to be met by ongoing surveillance at the site, the principal investigator will engage the head of Pharmaceutical Operations on site, or his/her designee, to

follow unblinding procedures (see **Section 6.3.3** for a description). To meet the criteria, the subjects must actually have received PfSPZ Vaccine and not NS placebo.

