- **Possibly Related** – There is some evidence to suggest a causal relationship (e.g., the event occurred within a reasonable time after administration of the trial medication). However, other factors may have contributed to the event (e.g., the participant’s clinical condition, other concomitant events). Although an AE may rate only as “possibly related” soon after discovery, it can be flagged as requiring more information and later be upgraded to “probably related” or “definitely related”, as appropriate.
- **Unlikely related** – A clinical event, including an abnormal laboratory test result, whose temporal relationship to study intervention administration makes a causal relationship

improbable (e.g., the event did not occur within a reasonable time after administration of the study intervention) and in which other drugs or chemicals or underlying disease provides plausible explanations (e.g., the participant's clinical condition, other concomitant treatments).

- **Not Related** – The AE is completely independent of study intervention administration, and/or evidence exists that the event is definitely related to another etiology. There must be an alternative, definitive etiology documented by the clinician.]

Expectedness

Principal investigators or designees will be responsible for determining whether an adverse event (AE) is expected or unexpected. An AE will be considered unexpected if the nature, severity, or frequency of the event is not consistent with the risk information previously described for the study intervention.

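### The one-child SAE pausing check tells the principal investigator that child's arm, contrary to section 7.3.3, and the available text does not protect the relatedness grade afterwards

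*Protocol*

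**What the plan says.** The pausing criteria stand under protocol 8.1, in a subsection numbered 7.1.1 and headed Pausing Criteria, Unblinding and Safety Hold (the pausing section below).

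- **First criterion.** The same related grade 3 event, or the same grade 3 laboratory abnormality, in at least 5% of vaccinees enrolled to date, with a minimum of three affected.
- **Second criterion.** "One participant experiences an SAE deemed possibly, probably or definitely related to study product". The text adds: "This criterion will not be met if it turns out that the participant received NS".
- **Both criteria.** "To meet the criteria, the subjects must actually have received PfSPZ Vaccine and not NS placebo".
- **The check (7.3.3).** The PI, described as still blinded, sends the list and states how many of those listed must be vaccinees. The head of Pharmaceutical Operations looks up the assignments and will "inform the principal investigator if the pausing criteria have been met, but will not unblind the principal investigator with respect to individual participants".
- **The blind (7.3.2).** "Blinding will continue until completion of the last study visit" and the data set is cleaned and locked. The PI is responsible for keeping the blind on site.
- **After confirmation.** The pausing section still leaves it to the DSMB to recommend whether affected children or caregivers should be unblinded. Section 11.5 has the sponsor tell the DSMB of every unblinding, intended or not.
- **Relatedness (9.11.3).** The examining investigator assigns it. For an event first graded possibly related, "it can be flagged as requiring more information and later be upgraded".
- **Endpoint (10.4.2; SAP 3.1).** The primary safety endpoint counts SAEs that are at least possibly related, and these SAEs are also tabulated by relatedness. Section 10.1 states that no formal hypothesis test is attached to it.

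**The concern.** The PI is promised a reply about a criterion and not about a child. With one child on the list the two are the same thing: *met* means vaccine and *not met* means saline. The protocol therefore claims a blinding property that its own rule removes in the check most likely to involve a serious event.

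Two things are at stake. First, relatedness decides whether an SAE enters the primary safety endpoint, and it is a clinical judgement made on the investigator side. If the grade can be changed after the arm is known, the reported grade is no longer certain to be a blinded one. Second, because 7.3.3 says that no individual is unblinded, the disclosure may never be logged or reported to the DSMB under 11.5.

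**Working it through.** **1. What a reply discloses.** Inputs: allocation from 7.3.1 ("Randomization will occur in blocks at 1:1 into vaccine or placebo arms"), so the prior probability of vaccine is 0.5 for each child; *k* = children listed; *m* = vaccinees needed. Ignoring block structure,

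P(vaccine | met) = Σ (x/k)·C(k,x)·0.5^k ÷ Σ C(k,x)·0.5^k, both sums over x = m to k.

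For *not met* the sums run over x = 0 to m − 1.

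| k | m | P(met) | P(vaccine given met) | P(vaccine given not met) |
|---|---|---|---|---|
| 1 | 1 | 0.50 | 1.00 | 0.00 |
| 3 | 3 | 0.125 | 1.00 | 0.43 |
| 5 | 3 | 0.50 | 0.69 | 0.31 |
| 6 | 3 | 0.66 | 0.62 | 0.27 |
| 7 | 7 | 0.008 | 1.00 | 0.50 |

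The first row is the SAE criterion; the arm is fully disclosed by either reply. The other rows are the grade 3 criterion, where full disclosure needs k = m and a *met* reply. For k = m = 3, *not met* gives (0 + 3 + 6) ÷ (7 × 3) = 0.43. The floor of three governs only up to 3 ÷ 0.05 = 60 vaccinees. At about 134 vaccinees, 5% is 6.7, so seven are needed, and seven listed children are all vaccinees with probability 0.5^7 = 0.008.

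**2. What a later change of grade can do.** The check starts from an SAE already judged related.

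- Possibly to probably or definitely related (the change described in 9.11.3): the binary count is unchanged; the table by relatedness changes.
- Related to unlikely or not related: the count falls by one. The available text neither describes nor bars this.
- Unrelated to related: this cannot follow from the check, because an SAE graded unrelated does not trigger it.

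**3. Size of one downgraded SAE.** The plan's own figures first: the exact two-sided 95% upper bound for 0/120 is 1 − 0.025^(1/120) = 0.0303, against 0.030 in Table 14. For 1/120 it is the 97.5% point of Beta(2, 119) = 0.0456, against 0.046. Both agree. At 134 per arm the bounds are 0.0272 for 0/134 and 0.0409 for 1/134. Dropping the only related SAE in an arm thus moves its upper bound from 4.1% to 2.7%. Fisher's exact test for 1 v 0 gives p = 1.0, the same as no events.

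**4. How often the check would run.** The protocol gives no expected rate of SAEs judged related. For an assumed rate r in both arms, the chance of at least one check among 268 children is 1 − (1 − r)^268: 24% at r = 0.1%, 74% at 0.5% and 93% at 1%.

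**The case against.** The strongest reply is that this is a wording slip with little consequence. The triggering grade is given blinded. The reply goes to the PI, while 9.11.3 gives relatedness to the examining investigator, who may be someone else. Section 11.8.1 tracks every correction with time and author, so a changed grade could be traced. Section 7.3.3 calls itself an overview and defers to an unblinding SOP, and part of the SAE reporting section is not in the public text; a safeguard on causality may sit in either.

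Most of this stands, and it limits the impact. It does not remove the contradiction: as long as the PI receives the reply, no SOP detail can keep a one-child list blinded. An audit trail shows that a grade changed, but it does not say which grade the analysis uses.

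A reader might infer more: that relatedness for the primary safety endpoint is set unblinded, that a result of 0 v 0 could become 1 v 0 through this route, or that later SAEs in other children are graded with the arm known. The documents do not support these readings. The check follows the relatedness judgement. An SAE graded unrelated never reaches it. One child's arm does not disclose another's. A later related SAE in the same child does not alter a per-child proportion that already counts that child.

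**Conclusion.** The contradiction is certain and rests only on the pausing section and 7.3.3: a single-participant SAE check discloses that child's arm to the PI whichever reply is given. The grade 3 rule does so only for a *met* reply when the number listed equals the number needed.

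The consequence for the endpoint is narrower. What remains open is a later downgrade, or a changed relatedness category in the tables, made by someone who knows the arm. This holds as far as the available text goes; the unblinding SOP was not available. Each check concerns one child. One downgraded event moves an arm's upper bound by about 1.4 percentage points (4.1% to 2.7% at 134 per arm), with Fisher p at 1.0 either way, and section 10.1 treats the endpoint descriptively. The sponsor should correct it, because the blinding statement is wrong as written and the remedy costs little.

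**What to change.** Leave the pausing criterion unchanged and reconcile 7.3.3 with the pausing section, including its text on the DSMB's later recommendation about unblinding.

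1. Require the blinded causality grade to be entered, time-stamped and locked before the pharmacy check is requested. State in 10.4.2 and SAP 3.1 that this grade defines the primary safety endpoint and that any later change is reported separately.
2. Reword 7.3.3 to say that a one-child list, or a *met* reply when the number listed equals the number needed, discloses the arm.
3. Log each such case as an unblinding and notify the DSMB under 11.5.

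Handing later judgements on that child to another investigator would add little, since anyone who knows of the SAE can read the arm from whether a pause follows.

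The cost is wording in the protocol, SAP and unblinding SOP, and one time-stamped field. No participants or visits are added. The downside is that a later, better-informed causality change appears as supplementary and does not overwrite the primary grade.
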